7.4.5 Management of Drug-related Infusion Reactions

Since BMS-986207 and nivolumab contain only human Ig protein sequences, they are unlikely to be immunogenic and induce infusion or hypersensitivity reactions. However, if such a reaction were to occur, it might manifest with fever, chills, rigors, headache, rash, pruritus, arthralgia, hypotension, hypertension, bronchospasm, or other allergic-like reactions. All Grade 3 or 4 infusion reactions should be reported within 24 hours to the BMS Medical Monitor and reported as an SAE. Infusion reactions should be graded according to NCI CTCAE v4.03 guidelines.

Treatment recommendations for infusion reactions are provided below and may be modified based on local treatment standards and guidelines, as appropriate.

For Grade 1 symptoms (mild reaction; infusion interruption not indicated; intervention not indicated):

- Remain at bedside and monitor participant until recovery from symptoms. The following prophylactic premedications are recommended for future infusions: diphenhydramine 50 mg (or equivalent) and/or acetaminophen/paracetamol 325 to 1000 mg at least 30 minutes before study drug administrations.

For Grade 2 symptoms (moderate reaction requiring therapy or infusion interruption but responding promptly to symptomatic treatment such as antihistamines, nonsteroidal anti-inflammatory drugs, narcotics, corticosteroids, bronchodilators, IV fluids, or prophylactic medications indicated for \leq 24 hours):

- Stop the study drug infusion, begin an IV infusion of normal saline, and treat the participant with diphenhydramine 50 mg IV (or equivalent) and/or acetaminophen/paracetamol 325 to 1000 mg; remain at bedside and monitor participant until resolution of symptoms. Corticosteroid and/or bronchodilator therapy may also be administered as appropriate. If the infusion is interrupted, then restart the infusion at 50% of the original infusion rate when symptoms resolve; if no further complications ensue after 30 minutes, the rate may be increased to 100% of the original infusion rate. Monitor participant closely. If symptoms recur, then no further BMS-986207 or nivolumab will be administered at that visit.
- For future infusions, the following prophylactic premedications are recommended: diphenhydramine 50 mg (or equivalent) and/or acetaminophen/paracetamol 325 to 1000 mg should be administered at least 30 minutes before study drug infusions. If necessary, corticosteroids (up to 25 mg of hydrocortisone or equivalent) may be used.

For Grade 3 or 4 symptoms (severe reaction, Grade 3: prolonged [ie, not rapidly responsive to symptomatic medication and/or brief interruption of infusion]; recurrence of symptoms following initial improvement; hospitalization indicated for other clinical sequelae [eg, renal impairment, pulmonary infiltrates]; Grade 4: Life-threatening; pressor or ventilatory support indicated):

- Immediately discontinue infusion of study drug. Begin an IV infusion of normal saline and treat the participant as follows: recommend bronchodilators, epinephrine 0.2 to 1 mg of a 1:1000 solution for subcutaneous administration or 0.1 to 0.25 mg of a 1:10,000 solution injected slowly for IV administration, and/or diphenhydramine 50 mg IV with methylprednisolone 100 mg IV (or equivalent), as needed. Participant should be monitored until the Investigator is comfortable that the symptoms will not recur. Study drug will be permanently discontinued except for a Grade 3 infusion reaction that returns to Grade 1 in less than 6 hours. Investigators should follow their institutional guidelines for the treatment of anaphylaxis. Remain at bedside and monitor participant until recovery of the symptoms.

In case of late-occurring hypersensitivity symptoms (eg, appearance of a localized or generalized pruritus within 1 week after treatment), symptomatic treatment may be given (eg, oral antihistamine or corticosteroids).

7.4.6 Discontinuation Due to Hypersensitivity

Any single grade 5 hypersensitivity related event, or two grade 4 hypersensitivity related events (according to the NCI CTCAE v4.03) will require permanent discontinuation of drug administration for these participants and further enrollment in the study will be halted until a full safety assessment can be completed.

7.5 Preparation/Handling/Storage/Accountability

The IP should be stored in a secure area according to local regulations. It is the responsibility of the Investigator to ensure that IP is only dispensed to study participants. The IP must be dispensed only from official study sites by authorized personnel according to local regulations.

The product storage manager should ensure that the study treatment is stored in accordance with the environmental conditions (temperature, light, and humidity) as determined by BMS. If concerns regarding the quality or appearance of the study treatment arise, the study treatment should not be dispensed and contact BMS immediately.

Study treatment not supplied by BMS will be stored in accordance with the package insert.

Investigational product documentation (whether supplied by BMS or not) must be maintained that includes all processes required to ensure drug is accurately administered. This includes documentation of drug storage, administration and, as applicable, storage temperatures, reconstitution, and use of required processes (eg, required diluents, administration sets).

Storage facilities for controlled substances must be securely locked and substantially constructed, with restricted access to prevent theft or diversion, as applicable by local regulations.

Refer to the current version of the IB and/or Pharmacy Manual for complete storage, handling, and dispensing information.

Further guidance and information for final disposition of unused study treatment are provided in [Appendix 2](#) and the Pharmacy Manual.

7.5.1 Retained Samples for Bioavailability / Bioequivalence

Not Applicable.

7.6 Treatment Compliance

Study treatment compliance will be periodically monitored by Drug Accountability Concomitant Therapy.

7.6.1 Prohibited and/or Restricted Treatments

Prohibited and/or restricted medications taken prior to the first dose of study drug in the study are described below. Medications taken within 4 weeks prior to the first dose of study drug must be recorded on the CRF.

- Prior exposure to anti-TIGIT therapy
- Exposure to any investigational drug within 4 weeks of the first dose of study drug

- Any live/attenuated vaccine (eg varicella, zoster, yellow fever, rotavirus, oral polio and measles, mumps, rubella) during treatment and until 100 days post-last dose
- Administration of investigational SARS-CoV-2 vaccines is not allowed during the study. Participants may receive approved SARS-CoV-2 vaccines while continuing on study treatment at the discretion of the Investigator. Non-live SARS-CoV-2 vaccination is considered a simple concomitant medication within the study.
- Treatment of active SARS-CoV-2 infections or high-risk exposures, including use of investigational therapies, is allowed and should be discussed with the Medical Monitor.

The following medications are prohibited during the study (unless utilized to treat a drug related AE):

- Immunosuppressive agents
- Immunosuppressive doses of systemic corticosteroids (except as stated in [Section 6.2](#))
- Any concurrent anti-neoplastic therapy (ie, chemotherapy, hormonal therapy, immunotherapy, extensive, nonpalliative radiation therapy, or standard or investigational agents).

7.7 Treatment After the End of the Study

At the conclusion of the study, participants who continue to demonstrate clinical benefit may be eligible to receive BMS-supplied study treatment. Study treatment may be provided via an extension of the study (a rollover study requiring approval by responsible health authority and ethics committee or through another mechanism at the discretion of BMS).

7.7.1 Permitted Therapy

Participants are permitted the use of the following treatments:

- Topical, ocular, intra-articular, intra-nasal, and inhalational corticosteroids
- Adrenal replacement steroid doses \geq 10 mg daily prednisone equivalent
- A brief (less than 3 weeks) course of corticosteroids for prophylaxis (eg, contrast dye allergy) or for treatment of nonautoimmune conditions (eg, delayed-type hypersensitivity reaction caused by a contact allergen)

8. DISCONTINUATION CRITERIA

8.1 Discontinuation from Study Treatment

BMS reserves the right to terminate access to BMS supplied study treatment if any of the following occur: a) the study is terminated due to safety concerns; b) the development of the BMS-986207 is terminated for other reasons, including, but not limited, to lack of efficacy and/or not meeting the study objectives; c) the participant can obtain the study medications from a government sponsored or private health program. In all cases, BMS will follow local regulations.

- Participants MUST discontinue the IP (and nonIP at the discretion of the Investigator) for any of the following reasons:
- Documented disease progression as defined by RECIST v1.1 ([Appendix 5](#)) unless participants meet criteria for treatment beyond progression ([Section 5.1.4](#))
- Clinical deterioration while receiving active study therapy that, in the opinion of the Investigator, indicates that continued participation in the study is not in the best interest of the participant
- Protocol-defined reasons for permanent discontinuation ([Section 7.4.4](#))
- Any drug-related AE occurring at any time that meets DLT criteria as outlined in [Section 7.4.1](#) will require permanent discontinuation unless the Investigator determines that only 1 of the agents must be discontinued due to toxicity attributed to that agent alone. Exceptions to permanent discontinuation are listed in [Section 7.4.4](#).
- Participant requests to stop study treatment and/or participation in the study
- Any clinical AE, laboratory abnormality or intercurrent illness, which, in the opinion of the Investigator, indicates that continued participation in the study is not in the best interest of the participant
- Termination of the study by BMS
- Loss of ability to freely provide consent through imprisonment or involuntarily incarceration for treatment of either a psychiatric or physical (eg, infectious disease) illness. (Note: Under specific circumstances, a participant who has been imprisoned may be permitted to continue as a participant. Strict conditions apply and BMS approval is required.)
- Inability to comply with protocol
- Discretion of the Investigator
- Pregnancy
 - Individual participants with confirmed CR will be given the option to discontinue study therapy on a case by case basis after specific consultation and agreement between the Investigator and BMS Medical Monitor in settings where benefit/risk justifies discontinuation of study therapy.

Discontinuation of the study treatment for abnormal liver tests should be considered by the Investigator when a participant meets one of the conditions outlined in [Section 9.2.7](#) (p-DILI) or if the Investigator believes that it is in best interest of the participant.

Refer to the [Schedule of Activities](#) for data to be collected at the time of treatment discontinuation and required follow-up, and for any further evaluations that can be completed.

In the case of pregnancy, the Investigator must immediately, within 24 hours of awareness of the pregnancy, notify the BMS Medical Monitor/designee of this event. In most cases, the study treatment will be permanently discontinued in an appropriate manner (eg, dose tapering if necessary for participant safety). Refer to [Section 9.2.5](#) Pregnancy.

All participants who discontinue study treatment should comply with protocol specified follow-up procedures as outlined in [Section 2](#). The only exception to this requirement is when a participant withdraws consent for all study procedures, including post treatment study follow-up or loses the ability to consent freely (ie, is imprisoned or involuntarily incarcerated for the treatment of either a psychiatric or physical illness).

If study treatment is discontinued prior to the participant's completion of the study, the reason for the discontinuation must be documented in the participant's medical records and entered on the appropriate CRF page.

8.1.1 Discontinuation Due to Further Progression (Confirmed Progression)

A radiographic assessment should be performed at each scheduled tumor assessment, 4 to 6 weeks following initial disease progression, to determine whether there has been continued progressive disease or not. Participants should discontinue study therapy upon evidence of further progression, defined as an additional 10% or greater increase in tumor burden volume from time of initial progression (including all target lesions and new measurable lesions).

The tumor burden volume from time of initial progression should be used as the reference baseline for comparison with the postprogression assessment.

Any new lesion considered nonmeasurable at the time of initial progression may become measurable and, therefore, must be included in the tumor burden measurement according to the following:

- **For solid tumors:** New lesions are considered measurable at the time of initial progression if the longest diameter is at least 10 mm (except for pathological lymph nodes, which must have a short axis of at least 15 mm).

For statistical analyses that include the Investigator-assessed progression date, participants who continue treatment beyond initial Investigator-assessed, RECIST v1.1-defined progression will be considered to have Investigator-assessed progressive disease at the time of the initial progression event.

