As described in [Section 5.4.6](#), accumulating evidence indicates a minority of participants treated with immunotherapy may derive clinical benefit despite initial evidence of progressive disease. Participants will be permitted to continue on study drug for treatment beyond initial RECIST v1.1-defined progressive disease as long as they meet the following criteria:

- Investigator-assessed clinical benefit and no rapid disease progression
- Participant is tolerating study treatment
- Stable performance status
- Treatment beyond progression will not delay an imminent intervention to prevent serious complications of disease progression (eg, CNS metastases)
- Participant provides written informed consent prior to receiving additional BMS-986207, nivolumab, and ipilimumab treatment, using an ICF describing any reasonably foreseeable risks or discomforts, or other alternative treatment options.

The decision to continue treatment beyond initial Investigator-assessed progression should be discussed with the BMS Medical Monitor and documented in the study records. A follow-up scan should be performed within 4 to 6 weeks of original progressive disease to determine whether there has been a decrease in the tumor size or continued progression of disease. Subsequent scans should be performed every 12 weeks until further progression is determined. If the Investigator

feels that the participant continues to achieve clinical benefit by continuing treatment, the participant should remain on the trial and continue to receive monitoring according to the Schedule of Activities in [Section 2](#). For participants who continue study therapy beyond progression, further progression is defined as an additional 10% increase in tumor burden from time of initial progressive disease. This includes an increase in the sum of diameters of all target lesions and/or the diameters of new measurable lesions compared to the time of initial progressive disease. Nivolumab, ipilimumab, and BMS-986207 treatment should be discontinued permanently upon documentation of further progression.

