New lesions are considered measurable at the time of initial progression if the longest diameter is at least 10 mm (except for pathological lymph nodes which must have a short axis of at least 15 mm). Any new lesion considered non-measurable at the time of initial progression may become measurable and therefore included in the tumor burden if the longest diameter increases to at least 10 mm (except for pathological lymph nodes, which must have a short axis of at least 15 mm). In situations where the relative increase in total tumor burden by 10% is solely due to inclusion of new lesions which become measurable, these new lesions must demonstrate an absolute increase of at least 5 mm.

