1.1 Measurable Lesions

Measurable lesions must be accurately measured in at least 1 dimension (longest diameter in the plane of the measurement to be recorded) with a minimum size of:

- 10 mm by CT/magnetic resonance imaging (MRI) scan (CT/MRI scan slice thickness no greater than 5 mm)
- 10-mm caliper measurement by clinical examination (lesions that cannot be accurately measured with calipers should be recorded as non-measurable)
- 20 mm by chest X-ray
- Malignant lymph nodes: To be considered pathologically enlarged and measurable, a lymph node must be \square 15 mm in the short axis when assessed by CT scan (CT scan slice thickness is recommended to be no greater than 5 mm). At baseline and in follow-up, only the short axis will be measured and followed.

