3.2.1.2 When the Subject Has Only Non-Measurable Disease

- To achieve ‘unequivocal progression’ on the basis of the non-target disease, there must be an overall level of substantial worsening such that the overall tumor burden has increased sufficiently to merit discontinuation of therapy.
- A modest ‘increase’ in the size of 1 or more non-target lesions is usually not sufficient to qualify for unequivocal progression status.
- Because worsening in non-target disease cannot be easily quantified (by definition: if all lesions are non-measurable), a useful test that can be applied when assessing subjects for unequivocal progression is to consider if the increase in overall disease burden based on the change in non-measurable disease is comparable in magnitude to the increase that would be required to declare PD for measurable disease: that is, an increase in tumor burden representing an additional 73% increase in ‘volume’ (which is equivalent to a 20% increase diameter in a measurable lesion). Examples include an increase in a pleural effusion from ‘trace’ to ‘large’

or an increase in lymphangitic disease from localized to widespread or may be described in protocols as ‘sufficient to require a change in therapy’.

- If ‘unequivocal progression’ is seen, the subject should be considered to have had overall PD at that point.

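### Section 8.1.1 sets the stopping rule after progression on a tumour volume that nobody measures, and leaves out the 5 mm new-lesion condition in Section 5.1.4

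*Combined protocol and SAP*

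**What the plan says.** Section 5.1.4 (Treatment Beyond Progression) sets further progression at an additional 10% in tumour burden since initial progression and says how burden is counted: "This includes an increase in the sum of diameters of all target lesions and/or the diameters of new measurable lesions". It then limits the rule. When the 10% is "solely due to inclusion of new lesions which become measurable, these new lesions must demonstrate an absolute increase of at least 5 mm". Once further progression is documented, all three drugs stop permanently.

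Section 8.1.1, in the chapter on discontinuation criteria, gives its own definition of the same event: "defined as an additional 10% or greater increase in tumor burden volume from time of initial progression", counting target and new measurable lesions. It repeats the metric for the reference value: "The tumor burden volume from time of initial progression should be used as the reference baseline for comparison with the postprogression assessment". On new lesions it says: "Any new lesion considered nonmeasurable at the time of initial progression may become measurable and, therefore, must be included in the tumor burden measurement". It gives the size at which a new lesion counts ("New lesions are considered measurable at the time of initial progression if the longest diameter is at least 10 mm", or 15 mm short axis for a node) and no minimum growth.

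Appendix 5 (RECIST 1.1) is the only measurement method described. It is linear: "Measurable lesions must be accurately measured in at least 1 dimension", with target lesions followed as a sum of diameters. It mentions volume once, as an analogy for judging non-measurable disease (Appendix 5, Section 3.2.1.2).

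**The concern.** One stopping rule has two definitions, and nothing in the protocol says which prevails. They differ in two ways.

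- **Metric.** Section 5.1.4 uses diameters. Section 8.1.1 names volume twice, although no volume is collected.
- **New lesions.** Section 5.1.4 guards against stopping because a small new lesion has just crossed the measurability limit. Section 8.1.1 requires that lesion to be counted and has no such guard.

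The second difference remains if *volume* is simply read as diameter. Two sites reading the same scan, each following a different section, could make opposite decisions about permanently stopping study drug.

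**Working it through.** **Inputs.** The 10% threshold is in Sections 5.1.4 and 8.1.1. The 5 mm condition is in Section 5.1.4. The measurability limits are 10 mm longest diameter, or 15 mm short axis for nodes, in both sections. The volume-to-diameter conversion is in Appendix 5, Section 3.2.1.2. The lesion sizes and sums used below are assumed for illustration.

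**1. Reproduce the plan's own conversion.** Appendix 5 equates a 20% diameter increase with "that is, an increase in tumor burden representing an additional 73% increase in" volume. With growth equal in three dimensions, volume scales as diameter cubed: 1.20³ − 1 = 72.8%, which matches the stated 73%.

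**2. Convert a 10% volume increase to diameter.** The answer depends on how the lesion grows.

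| Growth assumed | Formula | Equivalent diameter increase |
|---|---|---|
| Equal in three dimensions (Appendix 5's assumption) | 1.10^(1/3) − 1 | 3.2% |
| Two dimensions | 1.10^(1/2) − 1 | 4.9% |
| Measured axis only | 1.10 − 1 | 10% (no gap) |

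Under the Appendix 5 assumption, a 100 mm sum would trigger at 3.2 mm under Section 8.1.1 read literally and at 10.0 mm under Section 5.1.4. In the other direction, a 10% diameter increase is 1.10³ − 1 = 33.1% in volume.

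**3. The missing 5 mm condition, with both sections read in diameters.** Let S be the sum at initial progression. Suppose the target lesions are stable and one new lesion was below 10 mm at that time, so it is not in S. It grows from 9 mm to 10 mm, becomes measurable and enters the burden at its full 10 mm:

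relative increase = 10 / S

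| S (mm) | Increase | Section 8.1.1 | Section 5.1.4 (lesion growth 1 mm, below 5 mm) |
|---|---|---|---|
| 60 | 16.7% | met | not met |
| 80 | 12.5% | met | not met |
| 100 | 10.0% | met | not met |
| 120 | 8.3% | not met | not met |

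The sections conflict whenever 10 / S ≥ 0.10, that is S ≤ 100 mm. For a node growing from 14 to 15 mm short axis, the increase is 15 / S and the conflict runs to S ≤ 150 mm.

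**4. Which reading of the 5 mm clause is right?** The clause could mean the lesion's own growth (1 mm here) or its whole contribution to the burden (0 to 10 mm). A lesion that has just become measurable is at least 10 mm, or 15 mm for a node, so on the second reading the condition is always satisfied and excludes nothing. The clause has an effect only if it means the lesion's own growth.

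**The case against.** The strongest reply is that a site would not be misled in practice. No volume is collected, and Section 8.1.1 itself judges new lesions by diameter, so an investigator would use diameters and the step 2 figures would describe something nobody computes. On new lesions, Section 8.1.1 is silent rather than contradictory. Section 8.1 and Sections 5.1.2.2 and 5.1.2.7 send the reader to Section 5.1.4, so its fuller rule can be taken to qualify the shorter one. Section 8.1.1 says participants should discontinue, Section 5.1.4 leaves room for the investigator's view of clinical benefit, and the Medical Monitor must agree to treatment beyond progression. The 9-to-10 mm example also needs stable target lesions and one reading of the 5 mm clause.

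Much of this stands. *Volume* is probably loose wording, the conversion range includes no gap at all, and oversight makes a wrong stop less likely. Two parts do not stand. Reading the 5 mm as the lesion's contribution to burden would leave that clause with no effect. And the precedence of Section 5.1.4 is only an inference: Section 8.1.1 is the section a site would open for this decision, it states a complete rule, and it does not refer back.

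**Conclusion.** The concern holds, at low severity. Section 8.1.1 is wrong as written: it names a metric the trial does not measure, and it omits a condition that Section 5.1.4 attaches to the same event. The omission is the more solid part. With both rules in diameters, the two sections give opposite answers for a new lesion growing from 9 to 10 mm at any sum up to 100 mm, or a node growing from 14 to 15 mm at any sum up to 150 mm. This assumes stable target lesions and that the 5 mm refers to the lesion's own growth. The size of the metric difference depends on growth geometry, from 3.2% in diameter to no gap.

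The consequence is limited to when drug is stopped in selected participants treated beyond progression. Section 8.1.1 dates progression at the initial event for analysis, and Appendix 5 closes best overall response at documented RECIST progression, so PFS and ORR do not change. The documents do not say how many participants would be affected.

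**What to change.** In Section 8.1.1, delete *volume* in both places and replace the free-standing definition with a cross-reference to Section 5.1.4. Further progression would then be a 10% increase, from initial progression, in the summed diameters of target and new measurable lesions. The 5 mm absolute increase would apply when newly measurable lesions alone account for the 10%. It would help to add to Section 5.1.4 that the 5 mm is the growth of the new lesions themselves since initial progression.

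The cost is protocol wording only. Sample size, scan schedule and analyses are unchanged.
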